## Statistical Analysis Plan

### 3.3 Subject Early Termination

Subject early termination reasons including deaths, withdrawals, lost-to-follow-up, etc. will be summarized at all scheduled visits.

### 3.4 Protocol Deviation

Protocol deviations will be summarized by deviation categories for subjects in whom a protocol deviation was reported.

### 3.5 Descriptive Endpoints or Additional Data

The following descriptive endpoints will be summarized as % events per valve-year. Major bleeding, thromboembolism, valve thrombosis, endocarditis and major paravalvular leak will be assessed at 5 years, and descriptively compared to 2 times the objective performance criteria as defined in ISO5840-2:2021 for mechanical heart valves. All-cause mortality and reintervention will be assessed at 5 years, and descriptively compared to acceptance criterion, as outlined below:

- Annualized rate of all-cause mortality (Acceptance criterion = 5% per valve-year)
- Annualized rate of reintervention (Acceptance criterion = 5% per valve-year)
- Annualized rate of major bleeding (OPC = 1.6% per valve-year)
- Annualized rate of thromboembolism (OPC = 1.6% per valve-year)
- Annualized rate of valve thrombosis (OPC = 0.1% per valve-year)
- Annualized rate of endocarditis (OPC = 0.3% per valve-year)
- Annualized rate of major paravalvular leak (PVL) (OPC = 0.3% per valve-year)

NYHA Classification will be assessed at baseline and annual visits.

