5.5 Subject Withdrawal and Discontinuation

Each subject enrolled shall remain in the clinical investigation until completion of the required follow-up period; however, a subject's participation in any clinical investigation is voluntary, and the subject has the right to withdraw at any time without penalty or loss of benefit. Conceivable reasons for discontinuation may include, but not be limited to, the following:

- Subject death
- Subject did not undergo the Regent MHV implant surgery within 60 days of enrollment
- Subject had an unsuccessful implant of the Regent MHV
- Subject voluntary withdrawal
- Subject lost-to follow-up as described below
- Subject's follow-up is terminated according to Section 3.3

Note: Subjects who undergo a surgical reintervention following the implant of the Regent MHV will not be withdrawn from the study as a consequence of the reintervention. Such subjects will continue follow-up until completing their last scheduled study visit unless withdrawn from the study for another reason.

Sites must notify the Sponsor of the reason(s) for subject discontinuation. Investigators must also report this to their respective IRB/EC as defined by their institution's procedure(s).

No additional follow-up is required or data recorded from subjects once withdrawn from the clinical investigation, except for the status (deceased/alive).

However, if a subject withdraws from the investigation due to problems related to the safety or performance of the device under observation, the Investigator shall ask for the subject's permission to follow his/her status/condition outside of the clinical investigation.

Lost-to-Follow-up

If the subject misses two consecutive scheduled follow-up time points and the attempts at contacting the subject detailed below are unsuccessful, then the subject is considered lost-to-follow-up. Site personnel shall make all reasonable efforts to locate and communicate with the subject (and document these efforts in the source documents), including the following, at each contact time point:

- A minimum of two telephone calls on different days over the specified follow-up windows to contact the subject should be recorded in the source documentation, including date, time and initials of site personnel trying to make contact.
- If these attempts are unsuccessful, the site should send a letter (certified if applicable) to the subject.

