8.2.3 Descriptive Endpoints

The following descriptive endpoints will be summarized as % events per valve-year. Major bleeding, thromboembolism, valve thrombosis, endocarditis and major paravalvular leak will be assessed at 5 years, and descriptively compared to 2 times the objective performance criteria as defined in ISO5840-2:2021 for mechanical heart valves. All-cause mortality and reintervention will be assessed at 5 years, and descriptively compared to acceptance criterion, as outlined below:

- Annualized rate of all-cause mortality (Acceptance criterion = [REDACTED])
- Annualized rate of reintervention (Acceptance criterion = [REDACTED])
- Annualized rate of major bleeding (OPC = 1.6% per valve-year)
- Annualized rate of thromboembolism (OPC = 1.6% per valve-year)
- Annualized rate of valve thrombosis (OPC = 0.1% per valve-year)
- Annualized rate of endocarditis (OPC = 0.3% per valve-year)
- Annualized rate of major paravalvular leak (PVL) (OPC = 0.3% per valve-year)

Valve dysfunction will be assessed by echocardiogram at 6 months and annual visits.

NYHA Classification will be assessed at baseline and annual visits.

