15.2 Foreseeable Adverse Events and Anticipated Adverse Device Effects

Risks associated with the specified device and procedure are bleeding, hemolysis, endocarditis, infections, thrombus, or thromboembolism, valve dehiscence, unacceptable hemodynamic performance (including: elevated pressure gradients, prosthesis patient mismatch or transvalvular regurgitation), paravalvular leak, hemorrhagic complications secondary to anticoagulation therapy, prosthetic failure (including: pannus ingrowth (NSVD), leaflet fracture/ escape/ split/ dislodgement, and entrapped leaflet/ stuck valve/ leaflet immobility, thrombocytopenia, heart block requiring pacemaker implant, adjacent cardiac structure interference, stroke, heart failure, myocardial infarction, or death as described in the IFU. Any of these complications may require reoperation or explantation of the device. There may be risks related to the device under investigation that are unknown at present. Likewise, the exact frequency of the risk may be unknown.

15.3 Residual Risks Associated with the Device Under Investigation, as Identified in the Risk Management Report / Risk Analysis Report

Risk analysis of the Regent MHV device has been performed in accordance with the Risk Analysis Plan [REDACTED] and Design Failure Mode Effect Analysis [REDACTED] to systematically identify potential hazards associated with the design and use of this device. Based upon bench testing and prior Abbott-sponsored clinical study data, all risks have been identified and mitigated as far as possible through application of appropriate controls and inspections and determined to be within acceptable levels.

Residual risks are likewise disclosed in the IFU in the form of clear instructions of what actions to take or to avoid, to avoid a hazardous situation of harm from occurring (contra-indications, warnings, and precautions). The anticipated AEs disclosed in the IFU provide further information to enable the user, and potentially the subject, to make an informed decision that weighs the residual risk against the benefit of using the device.

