Operated Valve Endocarditis: Operated valve endocarditis is any infection involving a valve on which an operation has been performed. The diagnosis of operated valvular endocarditis is based on one of the following criteria: (1) reoperation with evidence of abscess, paravalvular leak, pus, or vegetation confirmed as secondary to infection by histologic or bacteriologic studies; (2) autopsy findings of abscess, pus, or vegetation involving a repaired or replaced valve; or (3) in the absence of reoperation or autopsy, meeting of the Duke Criteria for endocarditis. Positive blood cultures are not required for the diagnosis of operated valve endocarditis. Culture-negative endocarditis should refer only to negative blood culture results and not just the absence of any proof of infection. Morbidities associated with active infection, such as valve thrombosis, thrombotic embolus, bleeding event, or paravalvular leak, are included under this category, but not counted in other categories of morbidity.

Clinical Investigation Plan

Reintervention: Reintervention is any surgical or percutaneous interventional catheter procedure that repairs, otherwise alters or adjusts, or replaces a previously implanted prosthesis or repaired valve. In addition to surgical reoperations, enzymatic, balloon dilatation, interventional manipulation, repositioning, or retrieval, and other catheter-based interventions for valve-related complications are also considered reinterventions. Indications for reintervention must be reported. Open surgical and percutaneous catheter reinterventions should be listed separately.

Valve Thrombosis: Valve thrombosis is any thrombus not caused by infection attached to or near an operated valve that occludes part of the blood flow path, interferes with valve function, or is sufficiently large to warrant treatment. Valve thrombus found at autopsy in a patient whose cause of death was not valve-related or found at operation for an unrelated indication should also be counted as valve thrombosis.

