##### 1.4.2 Primary Performance Endpoint

The primary performance endpoint is freedom from valve-related reoperation at 5 years.

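### Is 5% per valve-year, the same figure as for all-cause death, too lenient a criterion for reintervention?

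*SAP*

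**What the plan says.** SAP 3.5 expresses the descriptive event endpoints as percent events per valve-year and uses two kinds of yardstick. Five complications are "descriptively compared to 2 times the objective performance criteria as defined in ISO5840-2:2021 for mechanical heart valves". The OPCs are 1.6% for major bleeding, 1.6% for thromboembolism, 0.1% for valve thrombosis, 0.3% for endocarditis and 0.3% for major paravalvular leak.

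The other two endpoints have acceptance criteria: "Annualized rate of all-cause mortality (Acceptance criterion = 5% per valve-year") and "Annualized rate of reintervention (Acceptance criterion = 5% per valve-year"). Protocol 8.2.3 has the same structure, "All-cause mortality and reintervention will be assessed at 5 years, and descriptively compared to acceptance criterion", with both values blacked out.

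Three other places bear on the point:

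- Protocol Appendix II defines the event broadly: "Reintervention is any surgical or percutaneous interventional catheter procedure" that repairs, alters or replaces the prosthesis.
- Protocol 5.5 keeps re-treated subjects in the study: "Subjects who undergo a surgical reintervention following the implant of the Regent MHV will not be withdrawn from the study".
- SAP 1.4.2 sets a separate, narrower primary endpoint: "The primary performance endpoint is freedom from valve-related reoperation at 5 years".

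Protocol 8.6 rules out formal hypothesis testing.

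**The concern.** Death from any cause and re-treatment of the valve are different outcomes, and one shared figure suggests that the reintervention limit was not set on its own merits. It also looks generous beside other figures in the same section. Thrombosis, endocarditis and paravalvular leak are plain reasons to re-treat a valve, and their doubled OPC limits add up to far less than 5%. In addition, the visible text does not say whether the observed rate or a confidence limit is compared with 5%.

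At stake is what a statement that the criterion was met would tell the reader. Protocol 8.8 sends annual reports to the regulator in support of registration renewal. If a valve with a mediocre reintervention rate would nearly always meet the limit, the statement carries little information.

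**Working it through.** **Inputs.** The criterion is 5% per valve-year, and the OPCs are those in SAP 3.5. There are 200 implanted subjects (SAP 2.4) followed for 5 years (SAP 1.3), so at most 200 × 5 = 1000 valve-years. The values 700 and 850 are assumptions that allow for death and dropout. Event counts are taken as Poisson. No visible text derives the 5%, so there is no calculation in the plan to reproduce.

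**Scale against the OPC limits.** For the three complications, 2 × (0.1 + 0.3 + 0.3) = 1.4% per valve-year, and 5 / 1.4 = 3.57. If all five are added, 2 × (1.6 + 1.6 + 0.1 + 0.3 + 0.3) = 7.8%, which is above 5%. The ratio therefore depends on which complications are summed, and the plan sums none of them.

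**Scale as 5-year freedom.** With a constant hazard and first events only, freedom is exp(−5 × rate). At 5% it is exp(−0.25) = 0.779, at 3.5% exp(−0.175) = 0.839, and at 1.4% exp(−0.07) = 0.932.

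**Chance of meeting the criterion.**

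- Rule A compares the point estimate. The criterion is met if events ≤ 0.05 × valve-years, that is, at most 35, 42 or 50 events at 700, 850 or 1000 valve-years.
- Rule B requires the exact one-sided 95% upper limit to lie below 5%. This allows at most 25, 31 or 38 events.
- P(met) = P(X ≤ maximum), with X Poisson and mean = true rate × valve-years.

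| True rate per valve-year | Rule A: P(met) at 700 / 850 / 1000 | Rule B: P(met) at 700 / 850 / 1000 |
|---|---|---|
| 3.0% | 0.998 / 0.999 / 0.9997 | 0.838 / 0.881 / 0.935 |
| 3.5% | 0.983 / 0.987 / 0.993 | 0.593 / 0.636 / 0.729 |
| 4.0% | 0.918 / 0.924 / 0.947 | 0.327 / 0.343 / 0.416 |
| 4.2% | 0.868 / 0.871 / 0.902 | 0.241 / 0.245 / 0.301 |

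At a true 3.5% the flag probability is one minus these values: 0.7-1.7% under Rule A and 27-41% under Rule B. Under Rule A the limit still catches poor performance, being exceeded with probability 0.84-0.89 at a true 6% and 0.98-0.99 at 7%.

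**Effect of a stricter limit.** Take an illustrative 2% limit on the point estimate (at most 14, 17 or 20 events). It is met with probability 0.99 or more at a true 1% and 0.04-0.07 at 3%. At a true 1.5% it is missed by chance with probability 0.08-0.11. A lower limit discriminates at lower rates and also fails acceptable valves more often. Which balance is right depends on the rate expected for this device, which the visible text does not give.

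**The case for a change.** The strongest case for a change is this. The plan itself calls 5% an acceptance criterion, and the reports go to a regulator. Under the point-estimate reading, twice the 1.4% yardstick (2.8%) would meet the criterion with probability above 0.999 and three times (4.2%) with probability 0.87-0.90. The primary endpoint does not fully cover the gap, because it counts valve-related reoperation while reintervention also takes in catheter procedures. The remedy would be short: a separate number drawn from the Appendix III literature review, and one sentence naming the quantity compared.

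Some of this stands. The figures are right, the scope of reintervention is wider, and under Rule A the limit discriminates little below about 4%.

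The step from there to a different number does not stand:

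- **The yardstick is not the plan's.** Of the risks that it lists, Protocol 15.2 says "Any of these complications may require reoperation or explantation of the device". They include pannus, leaflet entrapment, dehiscence, hemolysis and bleeding. Conversely, many thromboses, infections and leaks never lead to reintervention. The 1.4% could be too low or too high.
- **The basis may already exist.** The literature results and expected outcomes of Appendix III and the primary performance criterion cannot be read in the public text. The 5% may have come from the very review that the remedy would use.
- **The consequence depends on the reading.** Under Rule B a true 4.2% meets the criterion with probability of only 0.24-0.30. The visible silence on the rule is weak evidence of an omission, because SAP 2.2.2 breaks off just after mentioning rates.
- **The remedy has no value to insert.** A cross-check against the primary criterion S through −ln(S)/5 needs the redacted S and an allowance of unknown size for the broader event. A change to Protocol 8.2.3 would also need ethics committee approval (Protocol 10.4) at up to 10 centers.

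**Conclusion.** No change to the plan follows. It is true that reintervention and all-cause death share a 5% per valve-year criterion, and that on a point-estimate reading a true rate of 3.5% would be flagged in only about 1-2% of studies. On a one-sided 95% upper-limit reading the figure is 27-41%. Both results assume 700-1000 valve-years and Poisson counts.

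The documents do not show that 5% is wrong. The 1.4% comparison is a scale check only, and the figures that could settle the matter are redacted. What remains is a judgement on how strict a descriptive limit should be, and little in the visible plan turns on it: there is no hypothesis test, and SAP 2.3.2 specifies no secondary endpoints. Valve-related reoperation is assessed by its own primary endpoint. Because the rate per valve-year is reported, a reader who sees 3% can judge it without the label. Stating which quantity was set beside 5% is a reporting detail that an analyst can supply.

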## 4.0 DOCUMENTATION AND OTHER CONSIDERATIONS

All analyses will be performed using SAS® for Windows, version 9.2 or higher.

## 5.0 ACRONYMS AND ABBREVIATIONS

Acronym or Abbreviation	Complete Phrase or Definition
CIP	Clinical Investigation Plan
CRF	Case Report Form
AE	Adverse Event
SAE	Serious Adverse Event
SAP	Statistical Analysis Plan

## Statistical Analysis Plan

Acronym or Abbreviation	Complete Phrase or Definition
MHV	Mechanical Heart Valve
KM	Kaplan-Meier
PMCF	Post-market Clinical Follow-up
COVID-19	Coronavirus Disease 2019

### 7.0 APPENDICE

**Abbott**

[figure not shown]
Study Name: Regent China PMCF

## Statistical Analysis Plan

Study Name: [Regent China PMCF](#)

## Statistical Analysis Plan

**Abbott**

Study Name: Regent China PMCF

## Statistical Analysis Plan

Study Name: [Regent China PMCF](#)

## Statistical Analysis Plan

[REDACTED]

[REDACTED]

[REDACTED]

[REDACTED]

Study Name: [Regent China PMCF](#)

## Statistical Analysis Plan
